A Review on the Outcome of Patient managed in One Stop Postmenopausal Bleeding Clinic in New Territories East Cluster, NTEC

Principal Investigator: [name] [name]

Co-investigators: [name] [name]

[name] [name]

[name] [name]

Department of Obstetrics and Gynaecology, the Chinese University of Hong Kong, Shatin, New Territories, Hong Kong.

Introduction:

Postmenopausal bleeding (PMB) is a common gynaecological complaint, accounting for up to 5 to 10 % of postmenopausal women being referred to gynaecological outpatient clinic (1, 2). It also comprised of up to 10% of our outpatient gynaecological referral. In general, 60 % of women with postmenopausal bleeding have no organic causes identified, whilst benign causes of PMB includes atrophic vaginitis, endometrial polyp, submucosal fibroid and functional endometrium. However, between 5.7 to 11.5% of women with postmenopausal bleeding have endometrial carcinoma (3, 4, 5), which is the fourth most common cancer among women (6), therefore, it is important to investigate carefully to exclude genital tract cancer.

In the past, often women with PMB require multiple clinic visits in order to reach a final diagnosis. This not only increase the medical cost as a whole, but also imposes an enormous stress and burden on patients, concerning about delayed or overlooked diagnosis of genital tract cancer.

A One-stop postmenopausal bleeding clinic has been established since February, 2002 by the Department of Obstetrics and Gynaecology, New Territories East cluster (NTEC) aiming at providing immediate assessment of women with postmenopausal bleeding in one single outpatient clinic assessment.

During the visit, a detailed history was taken in regarding the PMB and usage of hormonal replacement therapy or herbal medicine. A physical examination was performed and a cervical smear was taken if not been taken within a year. Transvaginal ultrasound (TVS) was then performed to measure the endometrial thickness (ET), examining ovaries then followed by an endometrial sampling. An outpatient hysteroscopy was performed only if TVS showed an ET \geq 5mm, or an abnormal endometrial appearance or unsatisfactory ET. Benign looking endometrial polyp would be removed during the outpatient hysteroscopy if possible.

At the moment, there was very limited local data (7, 8) and lack of the long term result. We aim to retrospectively evaluate the clinical outcome of postmenopausal bleeding patients who has attended One Stop Postmenopausal Clinic in order to formulate better care and counseling in future.

Objectives:

1. To analyze histopathology in relative to history and ultrasound findings in PMB women presented to One Stop Postmenopausal Bleeding Clinic at NTEC
2. To correlate the clinical findings of transvaginal ultrasonography (TVS) with outpatient hysteroscopy and endometrial assessment in The One Stop Postmenopausal Bleeding Clinic
3. To identify predictive and prognostic factors in women with PMB for possible use in triaging high risk patients

Methodology

A. Subjects

Postmenopausal women who attended the One Stop Postmenopausal Bleeding Clinic since year 2002

B. Methods

All women with postmenopausal bleeding presented to One-Stop PMB clinic were enrolled for analysis. Menopause was defined as the cessation of menses for more than 1 year. These patients had a thorough history taken. A physical examination was performed. A vaginal ultrasound was performed to determine uterine dimension, the endometrial thickness (ET) and exclude other adnexal pathology. An Endometrial sampling was taken afterward. An outpatient hysteroscopy, a 2.7mm or 2mm 30 degree rigid hysteroscope was then inserted into the uterine cavity using either CO2 or normal saline as distending medium to identify uterine pathology if TVS showed an ET \geq 5mm, or an abnormal endometrial appearance, or unsatisfactory ET. Benign looking endometrial polyps were removed during the outpatient hysteroscopy if possible. The management was determined by the finding on transvaginal ultrasonography and hysteroscopy. If surgery was indicated, appropriate surgery would be booked in the clinic. Patient was discharged from the clinic if the findings were normal. A call-back system was established to recall patients with abnormal pathology. A follow up appointment would be given in case of suspicious pathology or incomplete examination.

The data was transferred into a computer database which will be analyzed. Medical records of all patients who presented to our One- Stop clinic at New Territories East Cluster will be reviewed. Patient's demographic data, presenting symptoms, clinical assessments, investigations and treatments will be collected. If they had operations performed, surgical pathology, if any, will also be reviewed. The outcomes in terms of death or still being alive are also ascertained from the Computerized Medical System.

Data and Analysis

Data will be analysed using SPSS 22.0 (SPSS Inc., Chicago, IL, USA) program. For comparison of frequencies, chi-square test or or a two-sided Fishers' exact test will be used where appropriate. The Mann- Whitney U Test will be used to compare nonparametric data and the Kolmogorov-Smirnov test for correlation analysis with $P < 0.05$ as indication of significance.

Implication of Data

Postmenopausal bleeding (PMB) is a worrisome symptom that requires urgent investigation because of its association with genital tract malignancy. One-stop postmenopausal bleeding clinic is becoming a trend, which has been effective in reducing the number of hospital visits per patient as well as decreasing patient anxiety (9). The review of the results of our One Stop Clinic which allows us to have better understanding of our patient's characteristics, risk factors and underlying pathologies in causing PMB. These could provide a better local evidence for future clinical use and patient care. The data helps to provide the basis for further improvement and streamlining the service as well as finding new approaches in the organization of the service.

Reference

1. Munro MG, Southern California Permanente Medical Group's Abnormal Uterine Bleeding Working Group. Investigation of women with postmenopausal uterine bleeding: clinical practice recommendations. *Perm J*. 2014 Winter;18(1):55-70.

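### Objective 1 compares histology by ultrasound result, but that result also decided how fully pathology was sought, so part of the association for focal lesions is built in

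*Protocol*

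**What the plan says.** Protocol, Objectives, item 1: "To analyze histopathology in relative to history and ultrasound findings in PMB women presented to One Stop Postmenopausal Bleeding Clinic at NTEC". Methodology, B. Methods sets the population: "All women with postmenopausal bleeding presented to One-Stop PMB clinic were enrolled for analysis".

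The work-up has a common part and a conditional part.

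- **Common.** After the ultrasound, "An Endometrial sampling was taken afterward". No ET condition is attached, and both the Introduction and B. Methods place the sample before any hysteroscopy.
- **Conditional.** The Introduction states: "An outpatient hysteroscopy was performed only if TVS showed an ET" of at least 5 mm, with abnormal appearance or unsatisfactory ET as the other two triggers. B. Methods repeats the rule and describes polyp removal only within that branch: "or an abnormal endometrial appearance, or unsatisfactory ET. Benign looking endometrial polyps were removed during the outpatient hysteroscopy if possible".
- **Afterwards.** "The management was determined by the finding on transvaginal ultrasonography and hysteroscopy". Women with normal findings were discharged, those with abnormal pathology were recalled, and suspicious pathology or an incomplete examination led to follow-up. At data collection, "If they had operations performed, surgical pathology, if any, will also be reviewed".

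The Data and Analysis section compares frequencies by chi-square or Fisher's exact test. The protocol does not separate histology by the work-up that produced it.

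**The concern.** The ultrasound result is both the exposure in Objective 1 and the gate to the more searching reference standard. Below the trigger, a woman with normal findings has histology from the clinic sample alone. Above it, histology may also come from a polyp removed at hysteroscopy or from an operation that followed. This is differential verification: both groups have an outcome, but it was ascertained with unequal sensitivity. A complete-looking cross-table would hide that.

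The lesions most exposed are focal. The Introduction lists endometrial polyp and submucosal fibroid among the benign causes of bleeding. If hysteroscopy finds any that the sample misses, they will cluster in scan-positive women more than they truly do. Objective 3 seeks factors for triage and would inherit the distortion wherever histology is its outcome.

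**Working it through.** The protocol gives no sample size, prevalence, detection rate or event count, so there is no stated figure to reproduce. All rates below are assumptions, shown over a range.

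**1. Polyps, across the hysteroscopy trigger.** Suppose polyps are equally common on both sides (true risk ratio 1). Let *h* be detection with sampling plus hysteroscopy and *s* detection by sampling alone. Observed frequency = prevalence × detection, so the prevalence cancels and the observed risk ratio is *h*/*s*. With *h* = 0.90 and prevalence 10%:

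| *s* | Observed above v below | Risk ratio | Chance of P<0.05, 500 per group (assumed) |
|---|---|---|---|
| 0.10 | 9% v 1% | 0.90/0.10 = 9.0 | about 1.00 |
| 0.30 | 9% v 3% | 0.90/0.30 = 3.0 | 0.98 |
| 0.50 | 9% v 5% | 0.90/0.50 = 1.8 | 0.70 |
| 0.80 | 9% v 8% | 0.90/0.80 = 1.125 | 0.08 |

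The artefact disappears only when *s* = *h*. If the true ratio is not 1, the same factor multiplies it.

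**2. Apparent sensitivity of the scan for polyps.** If a share *q* of polyps truly lies in scan-negative women, apparent sensitivity = (1−*q*)*h* / [(1−*q*)*h* + *q s*]. With *q* = 0.20 the true sensitivity is 80%. With *s* = 0.10, for example, 0.72/(0.72 + 0.02) = 97%. For *s* = 0.30, 0.50 and 0.80 the results are 92%, 88% and 82%.

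**3. ET alone.** Some women with ET below 5 mm had hysteroscopy for abnormal appearance or unsatisfactory ET. If a share *f* of thin-ET polyps reached hysteroscopy this way, the risk ratio is *h*/[*f h* + (1−*f*)*s*].

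- *f* = 0.5: 0.90/(0.45 + 0.05) = 1.8 for *s* = 0.10; 0.90/(0.45 + 0.15) = 1.5 for *s* = 0.30.
- *f* = 0.8: 0.90/(0.72 + 0.02) = 1.22 and 0.90/(0.72 + 0.06) = 1.15.

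**4. Cancer.** With 98% detection on the full work-up and 80%, 90% or 95% on sampling alone, the ratio is 0.98/0.80 = 1.225, 0.98/0.90 = 1.09 or 0.98/0.95 = 1.03. With 99% against 85% or 95% it is 1.16 or 1.04.

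**5. Would restricting to hysteroscoped women repair it?** Take polyp prevalence 20% in both ET groups, and abnormal appearance in 60% of thin-ET women with a polyp and 5% of those without.

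- Thin-ET women reaching hysteroscopy: 0.20 × 0.60 + 0.80 × 0.05 = 0.12 + 0.04 = 0.16.
- Polyps found among them: 0.12 × 0.90/0.16 = 67.5%.
- Polyps found with ET of 5 mm or more: 0.20 × 0.90 = 18%.
- Risk ratio, thick v thin: 18/67.5 = 0.27, where the truth is 1.

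The restriction conditions on the trigger and can reverse the association.

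**The case against.** The strongest reply is that a common histological test already exists. Sampling is described for every woman, and the protocol's main worry is cancer, where step 4 shows little inflation. This stands: the point concerns unequal thoroughness, not absent verification, and bears mainly on focal lesions.

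Second, a reader might infer that every woman with a thin endometrium was sampled and discharged. The protocol does not say so. Discharge applied to normal findings, and neither recall nor follow-up is tied to ET. Recall does respond to pathology already seen, however, so it does not recover what the sample missed.

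Third, a reader might take a ratio of 3 to 9 as the bias in the ET association. That is the low-detection end of an assumed range, for the comparison across the whole trigger. Two of the three triggers can apply to thin-ET women, so the figure for ET alone is smaller (step 3).

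Fourth, the protocol describes outpatient removal of polyps only, so a submucosal fibroid reaches histology through surgery. The mechanism for fibroids is therefore less direct.

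Fifth, this is a retrospective review, the pathway cannot be changed, and stratified tables may sit in an analysis plan not shown. The protocol also nowhere claims that histology was ascertained alike in everyone. All fair. But the unequal work-up is set by the protocol's own pathway, no later analysis can recover lesions never looked for, and the source of each result must be captured at extraction if any plan is to use it.

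**Conclusion.** The point holds for the ultrasound result as a whole, and chiefly for endometrial polyps, with submucosal fibroids affected through surgery. The direction follows from the pathway as long as hysteroscopy adds detection to sampling. The size is not known from the documents: with 90% detection at hysteroscopy and 10% to 80% by sampling alone, the spurious risk ratio across the trigger runs from 9 down to 1.1. For ET alone it is smaller, for instance 1.15 to 1.8 on the assumptions in step 3.

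A reader might go on to conclude that ET is discredited as a triage factor for cancer. The documents do not support that. Every woman was to be sampled, and the assumed inflation for cancer is about 3% to 22%, most of it at the lower end unless sampling is poor. It is a limitation that the analysis should expose. It does not invalidate the review.

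**What to change.** - Add one extraction field for the source of each histology result: clinic sample, hysteroscopic polypectomy or surgical specimen.
- For cancer and hyperplasia, report the association with TVS and history twice: on the clinic endometrial sample, which is described for every woman and precedes hysteroscopy, and on the final diagnosis from all sources. Base conclusions about ET and triage on what holds under both.
- Do not read a difference in polyp or fibroid frequency across the hysteroscopy trigger as an ET association.
- Do not replace it with a simple ET comparison among hysteroscoped women, because thin-ET women in that group were selected for abnormal or unsatisfactory scans. Show focal lesions descriptively by trigger reason: ET of 5 mm or more, abnormal appearance, unsatisfactory ET.

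The cost is one field and one table. The ET association may look weaker, and focal lesions would be described by trigger reason without a test against ET. Clinical care is unaffected.

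### Death is recorded only as dead or alive in women entering at any time since 2002, and no listed test takes length of follow-up into account

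*Protocol*

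**What the plan says.** - **Entry.** The Introduction dates the clinic: "A One-stop postmenopausal bleeding clinic has been established since February, 2002". Methodology, A. Subjects takes "Postmenopausal women who attended the One Stop Postmenopausal Bleeding Clinic since year 2002" and gives no last entry date.
- **Death outcome.** Methodology, B. Methods: "The outcomes in terms of death or still being alive are also ascertained from the Computerized Medical System". No date of death, date last known alive or look-up date is named.
- **Purpose.** The rationale at the end of the Introduction is "At the moment, there was very limited local data (7, 8) and lack of the long term result". The aim follows: "We aim to retrospectively evaluate the clinical outcome of postmenopausal bleeding patients", with the intended use "in order to formulate better care and counseling in future". Objective 3 is "To identify predictive and prognostic factors in women with PMB for possible use in triaging high risk patients".
- **Methods.** Data and Analysis opens with "For comparison of frequencies, chi-square test" or Fisher's exact test. It adds Mann-Whitney for nonparametric data and Kolmogorov-Smirnov for correlation, with significance at P < 0.05. It does not mention time to death, censoring, person-time, a fixed horizon or adjustment for entry date.

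**The concern.** The reference list includes papers from 2016, so the protocol was written in that year or later. The first attenders then have about 14 years or more of potential follow-up, while the latest may have very little. Being dead at look-up means something different for these two groups.

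Two consequences follow.

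1. A pooled proportion dead depends on how long the entry window is and when the look-up happens. It is not a risk over a stated period, so it supplies neither the missing long-term result nor a figure for counselling.
2. If a factor became more or less common over the years, or its level drifted, women with and without it were observed for different lengths of time. A test on vital status then mixes the factor's effect with length of observation. It can make a null factor look prognostic or hide a real one. Objective 3 is meant to feed triage, so either error matters.

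**Working it through.** The protocol states no sample size, death rate, data-cut date or trend, so it has no figure to reproduce. Every input below is an assumption chosen to show the mechanism.

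**Inputs.** Death rate r = 0.02 per year, the same for all women. Follow-up is uniform from m to T years, with T = 15 and m = 0, 2 or 5, and censoring is administrative only. N = 2000. The early and late entrants are the two halves of the entry window. A binary factor has prevalence p1 in the early half and p2 in the late half. Tests are two-sided at 0.05.

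**Step 1: risk of death in a slice of follow-up from a to b.**

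Risk = 1 − (exp(−ra) − exp(−rb)) / (r(b − a))

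| m | early half | late half |
|---|---|---|
| 0 | 0.201 | 0.071 |
| 2 | 0.209 | 0.099 |
| 5 | 0.221 | 0.139 |

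**Step 2: crude risks for a null factor, prevalence 30% early and 15% late, m = 0.**

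- Share of early entrants among exposed: 0.30/(0.30 + 0.15) = 0.667. Among unexposed: 0.70/(0.70 + 0.85) = 0.452.
- Exposed: 0.667 × 0.201 + 0.333 × 0.071 = 0.158.
- Unexposed: 0.452 × 0.201 + 0.548 × 0.071 = 0.130.
- Crude odds ratio 1.25 (from unrounded risks), where the true effect is none. For m = 2 and m = 5 it is 1.19 and 1.12.

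**Step 3: chi-square rejection.** The noncentrality is (difference in risk)² / [p(1 − p)(1/n₁ + 1/n₀)], where p is the pooled risk. For m = 0, n₁ = 2000 × 0.225 = 450, n₀ = 1550 and p = 0.136. The noncentrality is 2.30 and rejection is 32.8%.

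| Prevalence, early to late | m = 0 | m = 2 | m = 5 |
|---|---|---|---|
| no shift | 5.0% | 5.0% | 5.0% |
| 25% to 20% | 8.0% | 6.9% | 5.9% |
| 27.5% to 17.5% | 17.3% | 12.9% | 8.8% |
| 30% to 15% | 32.8% | 23.1% | 13.7% |

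Simulation of the last row (20,000 runs per cell) gave 33.6%, 23.3% and 13.8%. A log-rank test in the same setting rejected in 5.3%, 5.0% and 5.0% (10,000 runs). Over death rates of 1 to 3% per year, N = 500 to 4000 and m = 0 to 5, chi-square rejection for the three shifts spans 5.1–13.9%, 5.5–40.7% and 6.1–73.5%.

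**Step 4: continuous factor.** Mann-Whitney of dead against alive, with a null normal factor whose mean falls 0.3 SD between entry halves, rejects in 24.0%, 16.7% and 10.7% for m = 0, 2 and 5. With no shift it rejects in about 5%.

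**Step 5: masking.** True hazard ratio 1.5, prevalence rising from 15% to 30%.

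| | m = 0 | m = 2 | m = 5 |
|---|---|---|---|
| crude odds ratio | 1.19 | 1.28 | 1.39 |
| chi-square power | 22% | 43% | 72% |
| log-rank power (simulated) | 83% | 88% | 93% |

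With no shift in prevalence, chi-square power is 87%, 91% and 95%. The loss therefore comes from the link with entry date, not from the use of a binary outcome as such.

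**Step 6: horizon, with no trend at all.** The Step 1 formula over the whole window gives these pooled proportions dead:

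| | m = 0 | m = 2 | m = 5 |
|---|---|---|---|
| T = 15 | 13.6% | 15.4% | 18.0% |
| T = 10 | 9.4% | 11.2% | 13.9% |

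The 5-year risk is 1 − exp(−0.02 × 5) = 9.5% in all six cases.

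**The case against.** The strongest objection is that the protocol commits to no mortality comparison. The sentence on death describes data collection, and no test is assigned to it. Triage in this clinic may well mean sorting by risk of cancer at presentation: the Introduction stresses excluding cancer, the titles of the two cited local studies concern detecting and predicting endometrial cancer, and Implication of Data does not mention survival. On that reading objective 3 uses index-visit outcomes, which this point leaves alone. This stands in part. The link to mortality is an inference from the word prognostic, the stated lack of long-term results, the aim of evaluating clinical outcome, and the fact that deaths are looked up at all.

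A second objection is that survival methods, a data cut and a censoring rule could sit in an analysis plan that is not at hand. That is possible. But the protocol itself gives the outcome as a status and names only tests that ignore time. A later plan could not use survival methods if the dates were never abstracted.

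A third objection is that the bias needs a factor that shifts with entry date, and none is identified. This is correct. The illustrative rejection rates run from negligible to severe and cannot size the problem here. The missing time horizon, however, needs no such shift.

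**Conclusion.** The point holds and should be fixed, with medium confidence. The part that does not depend on a trend is this: with unequal follow-up and a status-only outcome, the proportion dead has no time horizon. In the illustration it moves between 9.4% and 18.0% while the 5-year risk stays at 9.5%. The conditional part is that a factor related to entry date can be falsely flagged (14 to 33% instead of 5% for the largest shift shown, but only 6 to 8% for the smallest) or missed (power 22 to 72% against 83 to 93%). All these sizes rest on an assumed 2% annual death rate, 15-year maximum follow-up (10 years in the second horizon row) and, for the test results, 2000 women. The actual bias cannot be known from the protocol. Objectives 1 and 2 and predictors of cancer at the index visit are not touched.

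**What to change.** Abstract the date of first clinic visit, the date of death and the date last known alive, and set a data-cut date. Then add to Data and Analysis:

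> Survival from first clinic visit will be described by Kaplan-Meier, with estimates at stated time points (e.g. 5 years) and 95% CI. Prognostic factors for death will be assessed by log-rank test and Cox regression, censoring at the date last known alive or the data cut, whichever is earlier.

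Keep chi-square, Fisher and Mann-Whitney for index-visit comparisons such as histology, and do not apply them to vital status. If no mortality comparison is intended, say so and report survival by Kaplan-Meier only.

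The cost is slightly more data abstraction. The records and computerized system already under review are the natural source of the dates; this is an assumption, since the protocol does not list them. The analyses are standard in SPSS, the stated software.

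### The tests named for Objective 2 can show that TVS, hysteroscopy and histology are associated, but they do not measure agreement, accuracy or correlation

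*Protocol*

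**What the plan says.** Objective 2 in the protocol is "To correlate the clinical findings of transvaginal ultrasonography (TVS) with outpatient hysteroscopy and endometrial assessment". The Methods describe a single visit with TVS first; then, "An Endometrial sampling was taken afterward". Hysteroscopy is conditional. The Introduction says "An outpatient hysteroscopy was performed only if TVS showed an ET" of 5 mm or more, or if the endometrium looked abnormal or its thickness could not be measured satisfactorily. The Methods repeat this rule.

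The Data and Analysis section names four tests for the whole study:

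- Categorical data: "For comparison of frequencies, chi-square test", with a two-sided Fisher's exact test as the alternative.
- Other comparisons: "The Mann- Whitney U Test will be used to compare nonparametric data".
- Correlation: "the Kolmogorov-Smirnov test for correlation analysis", with a 0.05 significance threshold.

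No test is tied to a numbered objective. The section names no measure of agreement, diagnostic accuracy or correlation.

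**The concern.** The findings that Objective 2 relates to one another are paired: each woman contributes a TVS result, a sampling result and, if triggered, a hysteroscopy result. The useful questions about such data are how often the methods agree, and how often TVS misses or over-calls what histology or hysteroscopy shows. None of the four named tests estimates either.

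The one test given to correlation is also wrong for that task. Kolmogorov-Smirnov asks whether two distributions differ, or whether one distribution fits a reference. It does not use the link between two measurements on the same woman.

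An analyst who followed the section as written could report a very small P value for Objective 2 and still not be able to say how closely TVS matches the other two assessments.

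**Working it through.** The protocol states no sample size, lesion rate or within-woman correlation, so there is no figure of its own to reproduce. All counts and correlations below are assumptions chosen to show how the tests behave.

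**1. Association against agreement.** Let a = both methods positive, b = TVS only, c = comparator only, d = both negative, and n the total.

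- Chi-square = n(ad − bc)² / [(a+b)(c+d)(a+c)(b+d)]
- Observed agreement p_o = (a+d)/n
- Chance agreement p_e = [(a+b)(a+c) + (c+d)(b+d)]/n²
- Kappa = (p_o − p_e)/(1 − p_e)

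| a / b / c / d | Chi-square | P | p_o | p_e | Kappa |
|---|---|---|---|---|---|
| 80 / 70 / 40 / 110 | 300 × 6000² / (150 × 150 × 120 × 180) = 22.2 | about 2 × 10⁻⁶ | 190/300 = 63% | 0.50 | 0.27 |
| 20 / 80 / 0 / 100 | 200 × 2000² / (100 × 100 × 20 × 180) = 22.2 | about 2 × 10⁻⁶ | 120/200 = 60% | 0.50 | 0.20 |
| 5 / 95 / 95 / 5 | 200 × 9000² / 100⁴ = 162 | about 4 × 10⁻³⁷ | 10/200 = 5% | 0.50 | −0.90 |

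The smallest P value belongs to the table in which the methods almost always disagree. If the comparator in the first table is taken as the reference, sensitivity is 80/120 = 67%, specificity 110/180 = 61%, PPV 80/150 = 53% and NPV 110/150 = 73%. The chi-square P value conveys none of these.

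The test itself is not faulty. Applied to the cross-table with one entry per woman, it rejected in 5.0% of 20,000 simulated tables when the two findings were unrelated (n = 300, both rates 30%).

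**2. Kolmogorov-Smirnov and correlation.** The two-sample statistic depends only on the two marginal distributions. For a yes/no finding it equals |b − c|/n. In the table 5/95/95/5 it is 0, with kappa −0.90. In a table 100/0/0/100 it is also 0, with kappa 1. For continuous measurements, reshuffling one of them among the women leaves the statistic unchanged while destroying any correlation.

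**3. A conditional point: two-sample use on paired rates.** Suppose chi-square were used to compare the share of women positive by one method with the share positive by another. With equal true rates and within-woman correlation ρ, the variance of the difference is (1 − ρ) times what the two-sample test assumes. Its real size at nominal 5% is therefore 2[1 − Φ(1.96/√(1 − ρ))]:

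- ρ = 0: 5.0%
- ρ = 0.3: 1.9%
- ρ = 0.5: 0.56%
- ρ = 0.7: 0.04%

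In an assumed table 60/20/5/115, the rates are 80/200 = 40% and 65/200 = 32.5%. The unpaired chi-square gives P = 0.119 and Fisher's test P = 0.145; the exact McNemar test, on the 25 discordant women, gives P = 0.004. The error is conservative: P values are too large and power is lost, but false positives are not inflated.

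**4. What the hysteroscopy trigger does.** Under the clinic's rule every woman who has hysteroscopy is TVS-positive. A table of TVS rule against hysteroscopy then has an empty TVS-negative row, and neither kappa nor McNemar's test is informative. Only a lesion-by-lesion comparison works, and only in this TVS-selected group.

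**The case against.** - **Chi-square is legitimate here.** The objective says correlate, and a woman-level cross-table test of association is a fair reading of that word. This stands. The complaint is that association is all it delivers.
- **No comparison of detection rates is planned.** A reader might infer from the phrase about comparing frequencies that TVS and hysteroscopy detection rates will be compared as independent samples, and conclude that the plan gives wrong P values. The protocol nowhere states that use and ties no test to an objective, so part 3 of the working is a caution, not an error found in the plan. Its figures also assume unselected pairs, which the hysteroscopy group is not.
- **A separate analysis plan may hold the accuracy and agreement measures.** It may, and their absence from the protocol alone would be no finding. Nor does the 0.05 threshold show that only P values will be reported. The point rests on what the protocol does name: a set of tests that does not fit Objective 2, including one assigned to correlation that cannot measure it.
- **Kolmogorov-Smirnov may be a slip for a normality check, or be meant for comparing endometrial thickness between histology groups.** Either would be a legitimate use. The sentence as written says neither.

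**Conclusion.** The point holds in limited form. The findings are paired within women. Chi-square and Fisher can establish association only, and Kolmogorov-Smirnov is misassigned. Followed as written, the section leaves the useful part of Objective 2 unanswered: a P value near 2 × 10⁻⁶ is compatible with a kappa of 0.20 or 0.27. These figures rest on assumed tables, because the protocol gives no counts. The misfit between tests and objective does not depend on those assumptions.

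Two stronger readings are not supported: that the planned chi-square test is invalid, and that the study will report wrong P values for paired detection rates. The second would be true only under a use the protocol does not describe. The correction is worth making because it is cheap and bears directly on a stated objective.

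**What to change.** In Data and Analysis, add a short paragraph for Objective 2:

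- **TVS against histology, in all sampled women:** report sensitivity, specificity, PPV and NPV with 95% CI. Define TVS-positive by the clinic's existing rule (thickness of 5 mm or more, abnormal appearance, or unsatisfactory measurement).
- **TVS against hysteroscopy, in women who had both:** cross-classify by lesion, such as polyp or submucosal fibroid. Report kappa with 95% CI, and use McNemar's test for any difference in detection. State that the results apply only to women whose TVS triggered hysteroscopy.
- **Continuous or ordinal pairs:** replace Kolmogorov-Smirnov with a rank correlation.
- **Chi-square and Fisher:** keep them for comparing different groups of women and as tests of association; do not use their two-sample form on paired rates.

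The cost is a few sentences and a little extra analysis. Kappa and McNemar's test are standard SPSS crosstab options. No new data are needed, provided the reviewed records show which lesion TVS suggested; the protocol does not say whether they do, so this should be checked first.

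### The Kolmogorov-Smirnov test is named for correlation analysis, but it compares distributions and can neither measure nor test correlation

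*Protocol*

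**What the plan says.** The Data and Analysis section of the protocol assigns tests by purpose:

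- Frequencies: "For comparison of frequencies, chi-square test or or a two-sided Fishers' exact test will be used where appropriate".
- Non-normal data: "The Mann- Whitney U Test will be used to compare nonparametric data".
- Correlation: "the Kolmogorov-Smirnov test for correlation analysis", with P < 0.05 "as indication of significance".

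No correlation coefficient and no agreement measure is named anywhere in the protocol, and KS is not described as a check of normality.

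The section does not link the KS clause to an objective. The most plausible link is Objective 2: "To correlate the clinical findings of transvaginal ultrasonography (TVS) with outpatient hysteroscopy and endometrial assessment". These findings come from the same women. Under Methods, each woman has transvaginal ultrasound (TVS), then "An Endometrial sampling was taken afterward", and then hysteroscopy if her TVS result calls for it.

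**The concern.** Correlation concerns how two values move together within the same woman. The two-sample KS test asks whether two sets of values have the same distribution, and its one-sample form asks whether one set fits a given distribution. Neither form uses the pairing.

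This is not a detail that a protocol may leave to a statistical analysis plan. The protocol names a method, and the method does not answer the question it is given. An analyst following the text would report a P value as evidence for or against a correlation when it carries no information on that. The error can go either way: a strong correlation can be missed, and a mere difference in level between two measurements can be reported as a significant correlation. No estimate of strength would be available in either case.

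**Working it through.** **Inputs.** From the protocol: KS for correlation, significance at P < 0.05, measurements taken in the same women. The protocol gives no sample size and no distribution, so there is no figure of its own to reproduce. Sample sizes, distributions and shifts below are assumptions.

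**Step 1: what the statistic uses.** For values a₁…aₙ and b₁…bₙ,

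D = maxₓ |F(x) − G(x)|, with F(x) = (number of aᵢ ≤ x)/n and G(x) = (number of bᵢ ≤ x)/n.

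F depends on the a values alone and G on the b values alone. Shuffling the b values among the women leaves G, and so D and its P value, exactly unchanged. This needs no assumption about n or distribution. One example with 300 normal pairs and correlation 0.9:

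| | KS D | KS P | Spearman |
|---|---|---|---|
| Pairs intact | 0.03 | 0.999 | 0.90 |
| Pairs shuffled | 0.03 | 0.999 | −0.01 |

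**Step 2: how often it misleads.** Bivariate normal pairs with correlation ρ were exponentiated to give skewed values in mm (assumed median 5 mm, log-SD 0.7). The second margin was shifted by 0 or 0.3 SD on the log scale. 2000 runs per setting, level 0.05. Entries are the percentage of runs significant, KS / Spearman:

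| Setting | n = 100 | n = 200 | n = 500 | n = 1000 |
|---|---|---|---|---|
| ρ = 0, no shift | 5.7 / 4.4 | 5.4 / 4.8 | 4.9 / 5.0 | 4.8 / 5.7 |
| ρ = 0.3, no shift | 3.1 / 84.2 | 2.8 / 98.7 | 2.2 / 100 | 3.1 / 100 |
| ρ = 0.9, no shift | 0 / 100 | 0 / 100 | 0 / 100 | 0 / 100 |
| ρ = 0, shift 0.3 SD | 45.2 / 4.7 | 74.0 / 5.2 | 99.2 / 4.4 | 100 / 6.0 |

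With equal margins, KS becomes less likely to be significant as the correlation rises, because positively correlated samples have more similar empirical distributions than independent ones. A separate run with normal data and n = 300 shows the same: KS 5.3%, 2.9%, 1.0% and 0.0% at ρ = 0, 0.3, 0.6 and 0.9, against Spearman 4.9%, 99.9%, 100% and 100%. With one margin shifted by 0.5 SD, KS was significant in about 100% of runs at every ρ, including 0.

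**Step 3: the use in which KS is valid.** If endometrial thickness (ET) is split by a binary finding, KS is a proper two-group comparison. With the finding present in 30% (assumed), KS / Mann-Whitney, % significant:

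| Shift | n = 200 | n = 500 |
|---|---|---|
| 0 | 4.5 / 4.5 | 4.9 / 4.6 |
| 0.5 SD | 78.5 / 87.8 | 99.3 / 99.8 |
| 0.8 SD | 99.7 / 99.8 | 100 / 100 |

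The level is right, but this is a group comparison. It yields no correlation, and for a shift in level the Mann-Whitney test in the same sentence already does it at least as well.

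**Step 4: a limit on any replacement.** According to the Introduction, "An outpatient hysteroscopy was performed only if TVS showed an ET" of at least 5 mm, an abnormal-looking endometrium, or an ET that could not be satisfactorily assessed. I simplified this to an ET cut-off with 70%, 50% or 30% of women above it (assumed). A full-cohort Spearman coefficient of 0.48 then becomes 0.36, 0.31 or 0.26 in the selected women, and 0.68 becomes 0.54, 0.47 or 0.41. A correct coefficient therefore still describes only the women who had hysteroscopy.

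**The case against.** The strongest reply is that the harm depends on which variables KS would be applied to, and the protocol does not say. For Objective 2 the clear continuous measurement is ET, while hysteroscopy and histology give mainly categorical findings. Two continuous measurements in mm with similar margins are not a structure that the protocol describes for this objective. If the protocol means association when it speaks of correlation, KS on ET split by a binary finding is valid evidence of association under the wrong label. KS can also detect what Mann-Whitney does not. With equal medians and a log-SD ratio of 1.5 or 2.0 (30% positive, assumed), KS was significant in 26% and 76% of runs at n = 200, and in 69% and 99.9% at n = 500, against 8% to 10% for Mann-Whitney. Finally, KS may have been meant as a normality check.

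Much of this stands as a limit on scope. The simulated percentages illustrate how the test behaves and do not forecast the study's results. The advantage of Mann-Whitney is confined to shifts in level. The categorical parts of Objective 2 are served by the planned tests.

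None of it rescues the clause. A two-group difference in distribution, in level or in spread, is still not a correlation. If a normality check was intended, the protocol does not say so, and correlation is then left with no method at all. The invariance in Step 1 holds whatever the variables.

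**Conclusion.** The concern holds: the clause is wrong as written. For paired measurements, a KS P value says nothing about correlation, and that conclusion is exact. The rates of misleading results (0% significant at correlation 0.9 with equal margins; 45% to 100% significant at correlation 0 with margins 0.3 SD apart) rest on the assumed sample sizes, distributions and shift.

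The damage is bounded. Association between categorical findings, and differences in ET between two groups, can still be tested as planned. What is lost is any valid correlation coefficient, and any test of one, for ordinal or continuous pairs. The clause should be corrected before analysis, but it does not undermine the review as a whole.

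**What to change.** In Data and Analysis, replace the KS phrase with wording such as:

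*Spearman's rank correlation coefficient (with 95% CI) will be used for ordinal or continuous pairs. Paired categorical findings will be cross-tabulated, with an agreement measure such as kappa only where both methods use the same categories. Any TVS-hysteroscopy correlation or agreement applies only to women selected for hysteroscopy by their TVS result.*

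The first sentence corrects the error. The other two keep the replacement from being applied to unsuitable data or over-read. If KS is retained, describe it only as a check of distribution.

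The cost is a change of wording in one place. The review is retrospective and no new data are needed.
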